10. STUDY CALENDAR

Baseline evaluations are to be conducted within 28 days of the start of protocol therapy with the exception of the bone marrow biopsy and lymph node biopsy which should be performed within 90 days of cycle 1, day 1. Assessments must be performed prior to the administration of any study agent. Study assessments and agents should be administered within \pm 3 days of the protocol-specified date, unless otherwise noted.

Trial period	Screening	Treatment Cycles									EOT	Post-treatment		
		To be repeated beyond 9 cycles until EOT unless otherwise noted												
Treatment cycle/name		1	2	3	4	5	6	7	8	9 ^l	30 days after last dose	60 days post-EOT	Follow-up ^d	Survival follow-up ^e
Scheduling window	-28 to -1	±3	±3	±3	±3	±3	±3	±3	±3	±3	(±10 days)	(±10 days)	Q12 weeks (±14 days) from last post-treatment visit	Q12 weeks (±14 days)
Informed consent	X													
Performance status	X	X	X	X	X	X	X	X	X	X	X	X	X	
Demographics	X													
Medical history	X													
Concurrent meds	X	X-----X												
Physical exam	X	X	X	X	X	X	X	X	X	X	X	X	X	
Vital signs including pulse oximetry	X	X	X	X	X	X	X	X	X	X	X	X	X ⁱ	
Height	X	X	X	X	X	X	X	X	X	X				
Weight	X	X	X	X	X	X	X	X	X	X			X	
Lymph node biopsy (archival or newly obtained biopsy)	X ^g		X ^g									X ^g		
Pembrolizumab		X	X	X	X	X	X	X	X	X				
CBC w/diff (auto or manual)	X	X	X	X	X	X	X	X	X	X	X	X	X	
Serum chemistry ^a	X	X	X	X	X	X	X	X	X	X	X	X	X	
HIV, HCV, HBV ^m	X													
EKG	X													
Adverse event evaluation		X-----X												
Blood for correlative studies ⁿ	X		X		X						X			
PET/CT and EBV viral load ^h	X		X		X				X ^f		X			
B-HCG	X ^b													
T3, Free T4, TSH ^o	X	X	X	X	X	X	X	X	X	X				
Urinalysis	X													
PT/INR and PTT	X													
Pulmonary function tests ^c	X													

Bone marrow biopsy and aspirate	X ^j			X ^k			X ^k			X ^k			
Survival status													X
a:	Comprehensive metabolic profile, LDH, phosphorus												
b:	Female subjects of childbearing potential should have a negative urine or serum pregnancy test within 72 hours prior to receiving the first dose of study medication. If the urine test is positive or cannot be confirmed as negative, a serum pregnancy test will be required.												
c:	FVC; FEF25-75; FEV1; DLCO; pulse oximetry; hemoglobin should be obtained within 3 days prior to PFTs; repeat PFTs are at investigator discretion												
d:	In subjects who discontinue therapy without documented disease progression every effort should be made to continue monitoring disease by radiographic imaging every 12 weeks (\pm 14 days) until one of the following occurs: start of new anti-cancer therapy; documented disease progression by investigator assessment; end of study; or death, whichever occurs first												
e:	After the start of new anti-cancer treatment or documented disease progression by investigator assessment, the subject will transition to the Survival Follow-up and the patient or their primary physician should be contacted by telephone or email every 12 weeks (+/- 14 days) to assess survival status												
f:	Patients who achieve a metabolic complete remission (defined as Deauville 1-3) may be followed subsequently with CT of the chest, abdomen, and pelvis rather than PET/CT at the discretion of the treating investigator; after cycle 9 radiology restaging will occur every 4 cycles (e.g. on cycles 13, 17, 21, etc) until cycle 33. There is a \pm 3-day window for radiology tests but radiographic restaging should occur prior to drug administration for a cycle on which restaging is due though this could include a scan the same day as but prior to dosing of study drug.												
g:	At screening, fresh biopsy (1 core) or archival tissue within 90 days of C1D1 (5 unstained slides, 5 μ m) is required, unless an exception is given by the study chair. Fresh biopsy samples at week 6 (\pm 7 days) and at the time of discontinuation due to disease progression are optional but highly recommended unless the tumors are considered inaccessible by the treating physician or concerns that a biopsy is contraindicated due to safety concerns.												
h:	In subjects with an unconfirmed PD assessment who continue study therapy a radiology assessment should be performed 12 weeks (\pm 7 days) from the time of unconfirmed PD assessment or at the time of treatment discontinuation. If a scan was previously obtained within 30 days of the time of treatment discontinuation then a repeat radiology examination is not required. Imaging should occur at any time that disease progression is suspected. Those who have EBV positive lymphoma will have EBV viral load assessed at screening. If positive, it will be subsequently checked at every disease assessment.												
i:	Pulse oximetry recommended but not required. Study drug should be held for pulse oximetry recording less than 94% when pulse oximetry is obtained during treatment.												
j:	Must be performed within 90 days of day 1 of therapy. Patients only require a bone marrow biopsy at screening if they have unexplained cytopenias of grade 2 or greater at baseline or if PET/CT is suggestive of bone marrow involvement.												
k:	Bone marrow biopsy only needs to be repeated to confirm CR												
l:	Up to 35 cycles												
m:	HIV 1/2 antibody, hepatitis B surface antigen, hepatitis B surface antibody, hepatitis B core antibody, hepatitis C antibody												
n:	Please refer to section 9.1 for more details												
o:	T3, Free T4 and TSH to be drawn every 3 cycles after cycle 9.												

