1.4 Exploratory Objectives

- To evaluate the expression of PD-L1, genetic integrity of PD-L1/2 locus, and latent viral infection in a selected subset tumors, and preliminarily correlate those with clinical outcome.
- To study the immune microenvironment and circulating lymphocyte subsets in patients before and after pembrolizumab, and preliminarily correlate those with clinical outcome.

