 - creatinine ≤ 1.5 times the normal upper institutional limit **OR** creatinine clearance $\geq 60 \text{ mL/min}/1.73 \text{ m}^2$ in participants with creatinine levels > 1.5 times the normal upper institutional limit
 - INR, aPTT or PT ≤ 1.5 times the ULN unless subject is receiving anticoagulation therapy as long as PT or aPTT are within therapeutic range of intended use of anticoagulant
- 3.1.9 Be willing to provide tissue from a newly obtained core needle or excisional biopsy. Newly-obtained is defined as a specimen obtained up to and including 90 days prior to treatment day 1. Subjects for whom newly obtained samples cannot be provided may be enrolled only with agreement by the overall PI.
- 3.1.10 No prior allogeneic transplant unless all of the following apply:
 - At least 5 years from time of transplant
 - Absence of clinically significant graft-versus-host disease (GVHD)
 - Not on immune suppression
 - Approval of overall PI

- 3.1.11 Not a candidate for potentially curative therapy at the time of enrollment
- 3.1.12 Measurable disease per the Lugano criteria.
- 3.1.13 Female subjects of childbearing potential should have a negative urine or serum pregnancy test within 72 hours prior to receiving the first dose of study medication. If the urine test is positive or cannot be confirmed as negative, a serum pregnancy test will be required.
- 3.1.14 Female subjects of childbearing potential must be willing to use an adequate method of contraception as outlined in Section 5.4.3 – Contraception for the course of the study through 120 days after the last dose of study medication.
Note: Abstinence is acceptable if this is the usual lifestyle and preferred contraception for the subject.
- 3.1.15 Male subjects of childbearing potential must agree to use an adequate method of contraception as outlined in Section 5.4.3- Contraception, starting with the first dose of study therapy through 120 days after the last dose of study therapy.
Note: Abstinence is acceptable if this is the usual lifestyle and preferred contraception for the subject
- 3.1.16 The effects of pembrolizumab on the developing human fetus are unknown. Should a woman become pregnant or suspect she is pregnant while she or her partner is participating in this study, she should inform her treating physician immediately.

3.2 **Exclusion Criteria**

- 3.2.1 Prior treatment with a PD-1, PD-L1 or PD-L2 inhibitor

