- 3.2.2 Has had a prior anti-cancer monoclonal antibody within 4 weeks prior to study day 1 or has not recovered (i.e., \leq grade 1 or at baseline) from adverse events due to a previously administered agent.
- 3.2.3 Participants who have had chemotherapy, targeted small molecule therapy, or radiotherapy within 2 weeks prior to study day 1 (6 weeks for nitrosoureas or mitomycin C) or who has not recovered (i.e., \leq grade 1 or at baseline) from adverse events due to previously administered agents. Note: subjects with \leq grade 2 peripheral neuropathy are an exception to this criterion and may qualify for the study.
- 3.2.4 Radiation therapy within 2 weeks of study treatment
- 3.2.5 Is currently participating and receiving study therapy or has participated in a study of an investigational agent and received study therapy or used an investigational device within 4 weeks of the first dose of treatment.
- 3.2.6 Has a known history of active tuberculosis.
- 3.2.7 Has known psychiatric or substance abuse disorders that would interfere with cooperation with the requirements of the trial.
- 3.2.8 Has an active infection requiring systemic therapy.
- 3.2.9 Has active autoimmune disease that has required systemic treatment in the past 2 years (i.e., with the use of disease modifying agents, corticosteroids, or immunosuppressive drugs). Replacement therapy (e.g., thyroxine, insulin, or physiologic corticosteroid replacement therapy for adrenal or pituitary insufficiency, etc.) is not considered a form of systemic treatment.
- 3.2.10 Has a diagnosis of immunodeficiency or is receiving any form of immunosuppressive therapy within 7 days prior to the first dose of trial treatment or is taking chronic systemic steroids (in doses exceeding 10 mg daily of prednisone equivalent) within 7 days prior to the first dose of trial treatment. Note: Subjects with asthma or chronic obstructive pulmonary disease that require intermittent use of bronchodilators, inhaled steroids, or local steroid injections are not excluded from the study.
- 3.2.11 Has a history of non-infectious pneumonitis that required systemic corticosteroid treatment or has active pneumonitis.

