9. BIOMARKER, CORRELATIVE, AND SPECIAL STUDIES

9.1 Correlative Studies

We will analyze tumors from pre-and on-treatment time points, when available. We plan to

analyze EBV expression, PD-L1 and PD-L2 expression, as well as PD-1 expression in the microenvironment. We will also perform FISH to assess the integrity of the PD-L1/2 locus. We will perform multi-parameter analyses of the tumor micro-environment. In addition, peripheral blood samples will be analyzed for absolute and relative amounts of various lymphocyte subsets. Those results will be correlated with responses, in an exploratory fashion. Those studies are subject to sample and funding availability.

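### The baseline blood for lymphocyte subsets may be drawn before the prior-therapy washouts are complete; a cycle 1 day 1 pre-dose draw would be a better baseline for this exploratory objective (minor)

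*Combined protocol and SAP*

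**What the plan says.** Section 1.4 sets the exploratory aim: "To study the immune microenvironment and circulating lymphocyte subsets in patients before and after pembrolizumab", with a preliminary correlation to clinical outcome. Section 9.1 adds that "peripheral blood samples will be analyzed for absolute and relative amounts of various lymphocyte subsets" and makes the work depend on samples and funding.

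Section 10 fixes the timing. The general rule is "Baseline evaluations are to be conducted within 28 days of the start of protocol therapy", together with "Assessments must be performed prior to the administration of any study agent". The row "Blood for correlative studies" is marked under Screening (day -28 to -1), is blank under cycle 1, and is next marked at a later treatment cycle. Its footnote sends the reader to Section 9.1, which gives no draw times.

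The washouts run from a different anchor:
- Section 3.2.3 excludes "Participants who have had chemotherapy, targeted small molecule therapy, or radiotherapy within 2 weeks prior to study day 1", with 6 weeks for nitrosoureas and mitomycin C.
- Section 3.2.10 excludes immunosuppressive therapy in the 7 days before the first dose, and chronic systemic steroids "in doses exceeding 10 mg daily of prednisone equivalent) within 7 days prior to the first dose of trial treatment".
- Section 3.2.2 sets 4 weeks before study day 1 for anti-cancer monoclonal antibodies.

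For tissue, Section 3.1.9 says: "Newly-obtained is defined as a specimen obtained up to and including 90 days prior to treatment day 1".

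**The concern.** A before/after comparison needs a baseline taken under the conditions in which treatment starts. Here the washouts protect day 1, while the baseline blood may be drawn up to 28 days earlier, and no text ties the draw to the end of a washout. A site could follow every rule and draw the sample while a patient is still receiving chemotherapy or chronic steroids.

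The later samples come from a different setting. Section 5.4.1 bars chemotherapy, immunosuppressants and, with listed exceptions, systemic glucocorticoids during treatment. An affected patient would thus contribute an on-drug baseline and a generally off-drug follow-up. If the earlier drugs alter circulating lymphocytes (a pharmacological assumption that the documents do not quantify), their withdrawal would be read as a pembrolizumab effect. The trial has one arm, so nothing internal separates the two. Section 13.6.2 plans no adjustment for time since prior therapy.

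**Working it through.** The plan gives no figure to reproduce on this point, so the check is day arithmetic.

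**Inputs.** Draw window: day -28 to -1 (Section 10). Washouts w, in days before day 1: 14 for chemotherapy, small molecules and radiotherapy, and 42 for nitrosoureas and mitomycin C (3.2.3); 7 for chronic steroids and immunosuppressants (3.2.10); 28 for antibodies (3.2.2). Cycle length: 21 days (5.1).

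**Convention.** Day -k lies k days before day 1. The last permitted dose of a prior drug falls on day -w.

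**Formulas.** Guaranteed drug-free gap at the draw: g = w - k. Zero or less means that the drug may still be given on or after the draw day. Number of allowed draw days with g of zero or less: 28 - w + 1 (none if w exceeds 28).

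| Prior treatment | w | Draw days with g ≤ 0 | g at day -28 | g at day -14 | g at day -7 | g at day -1 | g at C1D1 pre-dose |
|---|---|---|---|---|---|---|---|
| Chemotherapy, small molecule, radiotherapy | 14 | 28 - 14 + 1 = 15 (-28 to -14) | -14 | 0 | 7 | 13 | 14 |
| Chronic steroid >10 mg/day, immunosuppressant | 7 | 28 - 7 + 1 = 22 (-28 to -7) | -21 | -7 | 0 | 6 | 7 |
| Anti-cancer antibody | 28 | 28 - 28 + 1 = 1 (-28) | 0 | 14 | 21 | 27 | 28 |
| Nitrosourea, mitomycin C | 42 | 0 | 14 | 28 | 35 | 41 | 42 |

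If a dose exactly 14 or 7 days before day 1 counts as inside the washout, the last permitted days become -15 and -8. The counts then fall by one, to 14 and 21 of 28.

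At the extreme, a day -28 draw can precede the last chemotherapy by 14 days and the last steroid dose by 21 days. The antibody and nitrosourea rules leave essentially no such room.

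**Interval to the next sample.** If that sample is on cycle 2 day 1 (study day 22), the interval from the screening draw is 1 + 21 = 22 to 28 + 21 = 49 days. If it is on cycle 3 day 1 (study day 43), the interval is 1 + 42 = 43 to 28 + 42 = 70 days. In each case 1 to 28 of those days precede any pembrolizumab. With a C1D1 pre-dose baseline the interval is 21 or 42 days before visit windows, all of it after the first dose.

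**Reliability of the calendar cell.** The table columns may have shifted in the available text. PET/CT appears under cycles 2, 4 and 8, whereas Section 11.1 restages after cycles 2, 5 and 8. The on-treatment biopsy appears under cycle 2, while its footnote says week 6. Correcting those shifts moves on-treatment marks to later columns, so it does not create a cycle 1 draw. The blood count, chemistry and thyroid rows do carry a cycle 1 mark. The blank is the likelier reading, but the PDF should be consulted.

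**The case against.** **The schedule permits the problem; it does not produce it.** This stands. A draw on day -1 already has guaranteed gaps of 13 and 6 days. The counts of 15 and 22 are calendar days, not patients.

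**Affected blood samples can be identified.** This stands in part. Section 5.4.1 requires all medications from the 28 days before first dose to be recorded, the same span as the draw window, so a descriptive check by time since last drug is possible. None is planned. The blood count at cycle 1 gives total lymphocytes, not subsets.

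**The stakes are low.** This stands. The objective is exploratory and depends on funding, and Section 13.6.2 allows purely descriptive reporting. No primary, secondary or safety conclusion uses these samples.

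**A day 1 draw is also imperfect.** This stands. Recovery may continue after day 1, only 7 days after steroids, and there is no control arm.

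**Tissue is a separate matter.** This largely stands. The 90-day window is a deliberate eligibility rule, on-treatment biopsies are optional, and pairs will be scarce. A reader might infer that pairs with intervening therapy should be excluded, but that would discard an unknown number from a small set.

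A reader might also infer that patients needing steroids before day 1 have the worst prognosis, so that the correlation with outcome is biased. The documents describe neither bridging steroid use nor any link between such use and prognosis, so that inference has no support here.

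**Conclusion.** The point holds as a minor, optional improvement. Subject to confirming the calendar cell, the plan allows the baseline correlative blood to be drawn on or before the last permitted chemotherapy day (15 of 28 draw days) or the last permitted chronic-steroid or immunosuppressant day (22 of 28). In patients treated in that period, part of the before/after change in lymphocyte subsets could be withdrawal of those drugs.

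This rests on three things: the blank at cycle 1 is real, some patients receive such drugs in the last month before day 1, and those drugs affect circulating lymphocytes. The documents give neither the share of patients nor the size of the effect.

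It would go too far to conclude that the change necessarily mixes the two effects, or that the exploratory objective cannot be answered. Both depend on actual draw dates and prior treatment, which the plan leaves open. The primary response endpoint is unaffected.

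**What to change.** In Section 10, move the baseline mark for correlative blood from Screening to cycle 1 day 1, stated as pre-dose, alongside the blood count and chemistry already taken that day. The guaranteed drug-free gap at baseline becomes the full washout: 14 days for chemotherapy, small molecules and radiotherapy, and 7 days for chronic steroids and immunosuppressants. This changes one calendar cell and needs no extra visit or procedure. The draw must precede the infusion, since a missed pre-dose sample cannot be recovered.

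For tissue, keep all pairs. At most, add one CRF field that flags anticancer therapy given between biopsy and C1D1, and show paired results in Section 13.6.2 with and without the flagged pairs. The field is needed because the 28-day medication record leaves up to 90 - 28 = 62 days of the biopsy window uncovered. Medical history may hold earlier treatment, but no rule links it to the biopsy date.

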11. MEASUREMENT OF EFFECT

11.1 Response Criteria

The primary objective of this study is overall response rate (ORR). Response and progression will be evaluated following the 2014 Lugano criteria for the primary endpoint and LyRIC for secondary endpoint. Patients will undergo tumor restaging, using the appropriate combination of imaging and bone marrow biopsies, after cycles 2 and 5 and 8 and then every 4 cycles thereafter until cycle 32. Radiographic restaging will also be performed at the 60-day post-treatment follow-up visit and at pre-specified intervals thereafter (see Study Calendar, section 10). Imaging will consist of PET/CT scans until the patient has achieved a metabolic CR (defined as Deauville score 1-3) at which juncture transition to CT of the chest, abdomen and pelvis will be acceptable at the discretion of the treating physician. Response assessment will follow standard criteria (Lugano criteria) for lymphoma. Bone marrow biopsy will be required within 30 days of radiology testing to confirm CR for patients with marrow involvement at baseline. A repeat bone marrow biopsy is not necessary to confirm CR if there was no marrow involvement at baseline.

11.2 Evaluation of Best Overall Response

The best overall response is the best response recorded from the start of the treatment until disease progression/recurrence (taking as reference for progressive disease the smallest measurements recorded since the treatment started). The patient's best response assignment will depend on the achievement of both measurement and confirmation criteria.

11.2.1 Duration of Response

Duration of overall response: The duration of overall response is measured from the time measurement criteria are met for CR or PR (whichever is first recorded) until the first date that recurrent or progressive disease is objectively documented (taking as reference for progressive disease the smallest measurements recorded since the treatment started, or death due to any cause. Participants without events reported are censored at the last disease evaluation).

Duration of complete response: The duration of overall CR is measured from the time measurement criteria are first met for CR until the first date that progressive disease is objectively documented, or death due to any cause. Participants without events reported are censored at the last disease evaluation.

11.2.2 Progression-Free Survival

Overall Survival: Overall Survival (OS) is defined as the time from randomization (or registration) to death due to any cause, or censored at date last known alive.

Progression-Free Survival: Progression-Free Survival (PFS) is defined as the time from randomization (or registration) to the earlier of progression or death due to any cause. Participants alive without disease progression are censored at date of last disease evaluation.

For patients with progression of disease on imaging, it is strongly recommended that a confirmatory biopsy be obtained whenever possible.

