All concomitant medications received within 28 days before the first dose of trial treatment and 30 days after the last dose of trial treatment should be recorded. Concomitant medications administered after 30 days after the last dose of trial treatment should be recorded for SAEs and ECIs as defined in Section 7.2.

The exclusion criteria describe other medications which are prohibited in this trial.

There are no prohibited therapies during the post-treatment follow-up phase.

Nausea/vomiting: Nausea and vomiting should be treated aggressively, and consideration should be given in subsequent cycles to the administration of prophylactic antiemetic therapy per standard institutional practice. Subjects should be strongly encouraged to maintain liberal oral fluid intake.

Infection: Subjects with a documented infectious complication should receive oral or IV antibiotics or other anti-infective agents as considered appropriate by the treating investigator for a given infectious condition, according to standard institutional practice.

Cytopenias: growth factors and blood product transfusion support are allowed on this trial.

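### PFS and response duration treat a patient who changes therapy before progression differently depending on whether that patient later dies, which biases the Kaplan-Meier estimates

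*Combined protocol and SAP*

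**What the plan says.** Section 11.2.2: "Progression-Free Survival (PFS) is defined as the time from randomization (or registration) to the earlier of progression or death due to any cause". It adds: "Participants alive without disease progression are censored at date of last disease evaluation". Section 11.2.1 has the same structure for duration of response and duration of complete response: progression or death from any cause ends them, and "Participants without events reported are censored at the last disease evaluation". Section 13.6 analyses these endpoints by Kaplan-Meier. None of these sections, nor 13.5 or 13.7, says what happens when new anti-cancer therapy starts.

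The study calendar (section 10) does react to it. Under footnote d, imaging of patients who stop without progression continues until "start of new anti-cancer therapy; documented disease progression by investigator assessment; end of study; or death, whichever occurs first". Footnote e then moves them to telephone or email contact for survival only. Section 5.6 continues that contact for 24 months after treatment ends, and new therapy is not an off-study criterion in 5.7. Section 5.4.1 leaves later treatment open: "There are no prohibited therapies during the post-treatment follow-up phase".

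For response, section 11.2 says: "The best overall response is the best response recorded from the start of the treatment until disease progression/recurrence". Section 11.1 says: "Radiographic restaging will also be performed at the 60-day post-treatment follow-up visit", and refers to the calendar for the schedule.

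**The concern.** After a switch without progression the plan stops looking for progression but goes on learning about deaths. It then uses the deaths and discards the event-free time of the survivors. Kaplan-Meier assumes that censoring carries no information about outcome. Here, whether a switched patient is censored early is decided by whether that patient later dies.

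Switching without progression is foreseeable. Section 1.1 lists toxicity and sustained CR among the reasons to stop, Table 3 requires permanent discontinuation for several toxicities, and section 2.1 describes remission as the route to autologous transplant.

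At stake are the secondary estimates of PFS and response duration. They would mix the effect of pembrolizumab with that of later treatment. A death after transplant would shorten response duration, while a successful transplant would leave the risk set early.

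**Working it through.** **The plan's own figure.** No PFS or response-duration figure is stated, so there is none to reproduce. The response rule in 13.2.2 (at least 6 of 20, 15% against 40%) does reproduce: P(Bin(20, 0.15) ≥ 6) = 0.067 (stated 0.07) and P(Bin(20, 0.40) ≥ 6) = 0.874 (stated about 87%).

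**Step 1: the rules applied to two patients.** Both have a clean last scan at month 6 and start new therapy at month 7 without progression.
- Patient A dies at month 20. By 11.2.2 this is a PFS event at month 20.
- Patient B is alive at month 30. With no scan after the switch, B is censored at month 6.

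The 20 - 6 = 14 months after the last scan count for A and not for B, although both had the same history at the switch. This follows from the text alone.

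**Step 2: size for PFS.** All inputs are assumptions: median 4 months to progression, median 8-12 months from progression to death, scans every 9 weeks, and switching unrelated to prognosis. Truth is the PFS that would be seen with continued scanning.
- 11-20% switching before progression: 12-month PFS is 0.18-0.22 as written, against a true 0.15-0.17. Single settings within this: 0.188 against 0.160 at 12% (2.8 points) and 0.195 against 0.160 at 17% (3.5 points). The overall excess is about 2-6 points.
- About 34% switching: 0.27 against 0.16, or 11 points.
- All switchers censored at the last scan before the switch: 0.15-0.17, close to the truth. If switching is related to prognosis, this estimate is itself off by about 1-5 points.

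A second simulation (12-week scans, progression dated exactly, 15-41% switching, death hazard after the switch 0.03-0.10 per month) gives 0.14-0.18 as written. The exact value is 0.5^(12/4) = 0.125, so the excess is again about 2-6 points. Uniform censoring gives 0.09-0.12 there. It is a little low because censoring goes back to a scan while progression does not. Counting new therapy as an event gives 0.03-0.09.

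The upward direction arises because switched patients who die stay at risk until death, with any earlier progression unseen.

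**Step 3: response duration can move the other way.** Constructed example of 8 responders, in months from response. Three are transplanted at month 4, of whom one dies at month 10 and two stay well. Three others progress at 5, 9 and 14. Two are ongoing at 24. The 12-month Kaplan-Meier estimate is:
- As written (two survivors censored at 4, so 6 at risk; events at 5, 9 and 10): 5/6 × 4/5 × 3/4 = 0.50.
- All three censored at 4 (5 at risk; events at 5 and 9): 4/5 × 3/4 = 0.60.
- Survivors' remissions followed (8 at risk; events at 5, 9 and 10): 7/8 × 6/7 × 5/6 = 0.625.

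**Step 4: response rate, worst case.** If one non-responder among 20 were certain to be credited with a later response, the chance of passing under the null would be P(Bin(19, 0.15) ≥ 5) = 0.144 instead of 0.067. This is conditional on that misattribution happening.

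**The case against.** Censoring at the last disease evaluation is an ordinary convention and, because imaging stops at the switch, already gives survivors the treatment proposed below. That is right: the survivors' rule is not the defect by itself. The defect is pairing it with deaths observed after scanning has stopped.

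The size is illustrative. No switching rate is given, and 3.1.5 and 3.1.11 restrict lymphoma entry to patients who have relapsed after, are ineligible for or have declined autologous transplant, and all entry to patients who are not candidates for potentially curative therapy at enrolment. The example in step 3 is therefore only an example. The PFS shift is also smaller than the sampling error: near 12-month PFS of 0.19, the 90% half-width is 1.645 × √(0.19 × 0.81/n), which is 0.13 for n = 24 and 0.12 for n = 30. These are secondary, uncontrolled endpoints with no decision rule. All of this stands, and it limits the importance of the point. It does not remove the dependence of censoring on outcome.

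A reader might infer that the primary response rate is compromised and its false-positive rate doubled. The documents do not support that. Section 11.1 refers to the calendar, whose footnotes end imaging at new therapy. Section 11.2 closes response at progression. Sections 5.1 and 5.4.1 bar other anti-cancer agents during treatment. A false responder would need to stop without progression, switch, be scanned afterwards and still be credited.

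A reader might also infer from 5.4.1 ("Concomitant medications administered after 30 days after the last dose of trial treatment should be recorded for SAEs and ECIs") that the date of a switch would be unknown. That sentence concerns concomitant medication. Footnotes d and e and the reporting windows in 7.3.3, 7.3.4.1 and 7.3.4.2 already require sites to know when new therapy starts. What is missing is an explicit data item.

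**Conclusion.** The point holds for PFS, duration of response and duration of complete response. As written, the definitions and the calendar together produce outcome-dependent censoring among patients who switch without progression. On the assumptions above, 12-month PFS is about 2-6 points too high with 11-20% switching. Response duration may be biased in either direction, so readers could not correct for it. The true size is unknown because the switching rate is unknown.

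For the response rate there is only a narrow opening: 11.2 does not close best response at new therapy, and 11.1 does not itself make the 60-day scan subject to footnotes d and e. The figure of 0.144 is a worst case given one certain false responder, not an estimate of error. The sample size, the threshold of 6 responders, alpha (0.067) and power (0.874) do not change. The correction should be made because it is cheap and these are stated secondary objectives.

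**What to change.** - **11.2.1 and 11.2.2:** censor every patient who starts new anti-cancer therapy before progression at the last disease evaluation before it, whatever happens later. Define new therapy to include transplant and consolidative radiotherapy. Add a sensitivity analysis that counts new therapy as an event.
- **11.2:** count only responses documented before new anti-cancer therapy.
- **11.1:** make the 60-day restaging explicitly subject to calendar footnotes d and e, so that the two sections agree.
- **Data collection:** record the type and start date of the first new anti-cancer therapy at the follow-up contacts already planned.

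The cost is a few sentences and one item on the case report form. Intervals become slightly wider, and some known deaths leave PFS and response duration, though they remain in overall survival. Uniform censoring is unbiased only if switching is unrelated to prognosis, which is doubtful for patients who stop for toxicity or go to transplant. The sensitivity analysis should therefore be reported beside the main estimate, with the number of patients who switched.
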